## 2.8 TCAC post-release procedures

### 2.8.1 TCAC post release contact

Post-release, a study team member will make contact with the participant within 1 week to update contact details and to review attendance at TCAC sessions.

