### 2.9 Outcomes and Ascertainment

#### 2.9.1 Feasibility of TCACs

The goal of this assessment is both to evaluate the feasibility of implementing the TCAC and of endpoint ascertainment for a larger clinical trial of TCAC implementation.

Specific feasibility considerations are:

- 1) The proportion of participants who are able to navigate to the TCAC as defined by success with intended first TCAC visit
- 2) Success of the study team to ascertain six month linkage to care status
- 3) Ability to use social capital and stigma index tools and assess HIV RNA level at six months.

Success will be based on *a priori* targets of  $\geq 90\%$  of those attempting to attend a TCAC session able to find the location, successful follow-up of  $\geq 75\%$  of participants, and viral load ascertainment for  $\geq 95\%$  of participants in care.

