**Table 2: Feasibility Indicators**

Numerator	Denominator	Measure
-----------	-------------	---------

Number with first TCAC visit	Total in TCAC arm	Proportion
Number in TCAC arm with visit first to a clinic (not TCAC)	Total in TCAC arm	Proportion
Number in TCAC at 6 months (at least 2 visits)	Number with first TCAC visits	Proportion
Number in TCAC at 6 months	Number in TCAC arm	Proportion
Number with no more than two missed visits in 6 months	Number in TCAC arm	Proportion
Proportion of all participants with successful 6month care ascertainment assessed	All study participants	Proportion
Proportion of all participants with 6 m social capital questionnaire and stigma scale	All study participants	Proportion
Proportion among those in care with 6m VL ascertainment	All study participants	Proportion

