## 2.9.2 Effectiveness of TCACs

**Primary outcome:** The primary outcome of this assessment is the proportion of participants with self-reported care at 6 months either in TCAC or DoH clinical care. Self-reported care at 6 months will be defined as – having at least two post-release HIV care visits 90 days apart with the last visit between 5 and 7 months from release. We will perform an analysis of retention in care at 6 months among all randomized individuals as an intent to treat analysis.

We will also perform an eligible for 6 month follow-up analysis. This analysis will exclude:

- Not released within 3 months of enrollment
- Re-incarcerated within 6 months of release
- Died within 6 months of release
- Withdrawn participation within 6 months of release

**Secondary outcomes:** We will also evaluate the effectiveness of TCACs compared to care-as-usual for the following secondary outcomes:

1. Verified in care at six months
2. Time to linkage to care
3. Linkage to care within 90 days of corrections release
4. HIV RNA <400 c/mL at 6 months - Viral load data at 6 months will be based on routinely collected viral load data (clinic records and the electronic National Health Laboratory System to determine 6 month viral load outcomes, successfully applied in prior studies) augmented by viral loads obtained by the study when 6 month viral load data are not available.
5. Social capital score change
6. Stigma index score change
7. Employment or self-employment

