**Table 3: Effectiveness outcomes**

Primary outcome	Self-reported in care at six months by arm	Test of proportions (chi-square)
Secondary outcomes	Self-reported linkage to care by 90 days by arm	Test of proportions (chi-square)
	Clinical record verified in care at six months by arm	Test of proportions (chi-square)
	HIV RNA <400c/mL for those in care by arm	Test of proportions (chi-square)
	Social capital score by arm	Test of medians (Wilcoxon rank sum)
	Stigma index score by arm	Test of medians (Wilcoxon rank sum)
	Employed or self-employed by arm	Test of proportions (chi-square)

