## 4.2 Analysis

### 4.2.1 Feasibility

Success will be based on *a priori* targets of  $\geq 90\%$  of those attempting to attend a TCAC session able to find the location, successful follow-up of  $\geq 75\%$  of participants (based on the challenging nature of follow-up of this population our prior work with 75% follow-up), and viral load ascertainment for  $\geq 95\%$  of participants in care.

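### Table 2 prints the wrong denominator for the 95% viral-load target and has no row with the denominator of the 90% navigation target

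*Combined protocol and SAP*

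**What the plan says.** Section 1.2 makes feasibility of implementation and of endpoint ascertainment the first primary objective. Sections 2.9.1 and 4.2.1 base success on three targets:

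- navigation: at least 90% "of those attempting to attend a TCAC session able to find the location";
- follow-up: at least 75% of participants;
- viral load: ascertained for at least 95% "of participants in care".

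Table 2 is where the indicators receive numerators and denominators. Its last row is labelled "Proportion among those in care with 6m VL ascertainment", while the denominator cell of that row names all study participants.

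On navigation, Section 2.9.1 describes reaching the TCAC "as defined by success with intended first TCAC visit". The closest row in Table 2 is "Number with first TCAC visit" over the total in the TCAC arm. The second row counts TCAC-arm participants who went first to a clinic, again over the whole arm. No row is restricted to those who attempted to attend. Section 2.5.2 says that TCAC participants are reminded before release of the place and time of their assigned session and are given a facilitator's number.

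On being in care, Section 2.9.2 defines the self-reported form as "having at least two post-release HIV care visits 90 days apart with the last visit between 5 and 7 months from release". Table 3 also lists "Clinical record verified in care at six months by arm", without a definition of its own.

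**The concern.** These targets decide whether the pilot counts as feasible, so each needs an indicator with the same denominator.

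For viral load, the row label and both statements of the target agree, and one cell contradicts them. An analyst who follows the cell computes a different quantity, one that mixes laboratory ascertainment with retention, and then sets it against a threshold meant for ascertainment alone.

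For navigation, the target asks whether people who tried to come could find the venue. Dividing first visits by the whole arm asks how many came at all. A participant who never tried lowers the second figure and does not enter the first. Since the plan does not say what counts as an attempt, the target has no settled denominator, and the uptake row is the figure most likely to be put in its place.

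**Working it through.** **Inputs.** 60 participants in care as usual and 120 in the TCAC arm, total 180 (Section 4.1, Table 4). Targets of 90%, 75% and 95% (Sections 2.9.1 and 4.2.1). The targets are chosen thresholds, so there is no formula behind them to reproduce. The nearest planning figure, 12 to 20 participants in each of four TCACs at 40 to 66% successful transition, does reproduce: 120 × 0.40 / 4 = 12.0 and 120 × 0.66 / 4 = 19.8.

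**Which targets have a matching row**

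| Target | Denominator in the target | Nearest row in Table 2 | Denominator in that row | Match |
|---|---|---|---|---|
| Follow-up, 75% | all participants | six-month care ascertainment | all participants | yes |
| Viral load, 95% | those in care | viral load among those in care | all participants | no |
| Navigation, 90% | those attempting | first TCAC visit | whole TCAC arm | no |

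**Viral load.** Let C be the number in care at six months and V the number of those with a viral load.

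- Target measure: V / C.
- Row as printed: V / 180 = (V / C) × (C / 180), which is at most C / 180.
- To reach 95% as printed, V must be at least 0.95 × 180 = 171. Check: 171/180 = 0.950 and 170/180 = 0.944. So at least 171 must be in care, all with a viral load.
- Comparison with the plan's own follow-up target: 0.75 × 180 = 135. If in-care status counts only where it has been ascertained (assumption), a trial that just meets 75% follow-up can show at most 135/180 = 75% on the printed row, even with every viral load obtained.
- Hypothetical illustration: suppose 44% are in care, borrowing the prior cohort's ART continuity from Section 1.1. Then C = 0.44 × 180 ≈ 79. A trial with V = 76 meets the target (76/79 = 96.2%) but prints 76/180 = 42.2%.

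**Navigation.** Let A be the number who attempt and F the number who find the session. For this comparison, take F as the number with a first TCAC visit.

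- Target measure: F / A.
- First-visit row: F / 120 = (F / A) × (A / 120). The two are equal only if A = 120.
- With F / A exactly 0.90, and 40%, 66% or 100% of the arm attempting (hypothetical shares), the row shows 0.90 × 0.40 = 36%, 0.90 × 0.66 = 59%, or 90%.
- Even if all 120 attempt, the target allows at most 12 failures: 108/120 = 0.900 and 107/120 = 0.892. With fewer attempters it allows fewer, so the result turns on a small count and on what is called an attempt.

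**The case against.** **The viral-load cell is a slip that nobody would follow.** In the last three rows of Table 2 the numerator cell already holds a whole proportion, so the third cell may have been meant as scope (both arms) and not as a divisor. This explains how the entry could have arisen, and the intended meaning is not in doubt. But the column is headed as the denominator, and in the two rows directly above the same entry is the true divisor. The cell is still wrong as written, and it sits behind a success threshold. The percentages that borrow the 44% figure show what a literal calculation would give and do not forecast a result.

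**The in-care definition is already settled.** This largely stands. The self-reported definition serves the primary outcome and is the natural default. The record-verified form in Table 3 is only a label, so pointing to it would leave the term undefined.

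**The navigation target has more support than Table 2 shows.** Section 2.5.2 gives the intended first visit a plausible referent, namely the assigned session. The row on clinic-first visits also bears on navigation, and the plan does not promise that Table 2 lists every target. All of this is fair. It does not say what an attempt is, and a clinic-first visit is not a failed attempt to find the TCAC.

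**Two stronger readings are tempting.**

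- A reader might infer that failed attempts will go unrecorded. The documents do not support this. In Section 2.8.1 a team member is to "make contact with the participant within 1 week to update contact details and to review attendance at TCAC sessions". Sections 2.8.3 and 2.8.10 add a text after a missed session and a call or home visit to non-reporters. Participants hold a facilitator's number, and Table 5 lists contact, health-seeking and no-clinic-visit forms. None is described as recording an attempt, but the questions on the forms are not supplied.
- A reader might infer that first-visit uptake is planned at 40 to 66% and so is bound to fail 90%. Section 4.1 gives that range as successful transition in care to TCACs, used to size the clubs. First-visit uptake could be higher.

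**Conclusion.** The point holds, and should be fixed, for two of the three targets; the follow-up target has a matching row. The viral-load cell is an error as written: on that denominator, 95% requires at least 171 of 180 participants in care with complete viral-load ascertainment. This rests only on the planned total of 180. The 95% target itself, as worded in Sections 2.9.1 and 4.2.1, is sound.

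The navigation gap is secondary. It consists of an undefined term and a missing row, and the uptake row can replace the target measure only if all 120 in the TCAC arm attempt to attend. Whether attempts are captured is a matter to confirm, not a finding. Figures that use 44% or 40 to 66% are illustrations and carry none of the conclusion. No power, sample-size or effectiveness result changes.

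**What to change.** 1. In the viral-load row of Table 2, change the denominator to participants in care at six months, and state that the self-reported definition of Section 2.9.2 applies.
2. Add a row to Table 2 for the 90% target: TCAC-arm participants who found the session, over those who attempted to attend. Define an attempt, for example having tried to reach the assigned session of Section 2.5.2.
3. Before follow-up data are collected, confirm that an existing post-release contact form asks whether the participant tried to attend a TCAC session (yes/no) and found it (yes/no). If none does, add that item to one of them.
4. Keep first visit over the TCAC arm as an uptake indicator, and do not judge it against 90%.

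The cost is one cell, one row with its definition, and at most one form item. Design, sample size and the effectiveness analysis stay as they are.

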## 2.9.2 Effectiveness of TCACs

**Primary outcome:** The primary outcome of this assessment is the proportion of participants with self-reported care at 6 months either in TCAC or DoH clinical care. Self-reported care at 6 months will be defined as – having at least two post-release HIV care visits 90 days apart with the last visit between 5 and 7 months from release. We will perform an analysis of retention in care at 6 months among all randomized individuals as an intent to treat analysis.

We will also perform an eligible for 6 month follow-up analysis. This analysis will exclude:

- Not released within 3 months of enrollment
- Re-incarcerated within 6 months of release
- Died within 6 months of release
- Withdrawn participation within 6 months of release

**Secondary outcomes:** We will also evaluate the effectiveness of TCACs compared to care-as-usual for the following secondary outcomes:

1. Verified in care at six months
2. Time to linkage to care
3. Linkage to care within 90 days of corrections release
4. HIV RNA <400 c/mL at 6 months - Viral load data at 6 months will be based on routinely collected viral load data (clinic records and the electronic National Health Laboratory System to determine 6 month viral load outcomes, successfully applied in prior studies) augmented by viral loads obtained by the study when 6 month viral load data are not available.
5. Social capital score change
6. Stigma index score change
7. Employment or self-employment

**Table 3: Effectiveness outcomes**

Primary outcome	Self-reported in care at six months by arm	Test of proportions (chi-square)
Secondary outcomes	Self-reported linkage to care by 90 days by arm	Test of proportions (chi-square)
	Clinical record verified in care at six months by arm	Test of proportions (chi-square)
	HIV RNA <400c/mL for those in care by arm	Test of proportions (chi-square)
	Social capital score by arm	Test of medians (Wilcoxon rank sum)
	Stigma index score by arm	Test of medians (Wilcoxon rank sum)
	Employed or self-employed by arm	Test of proportions (chi-square)

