## 1.2 Study objectives

The overarching goal of this study is to tailor and pilot a transition community adherence club (TCAC) strategy for HIV-positive individuals transitioning from correctional to community settings in South Africa. The current proposal will allow for developing and piloting of the TCAC strategy to assess the feasibility for a fully powered effectiveness randomized clinical trial (RCT) comparing the TCAC to traditional care with a primary outcome of being in care with an undetectable viral load six months after release.

The primary objectives of this study are:

1. To assess the feasibility of implementing TCACs and of endpoint ascertainment

2. To assess the effectiveness of TCACs compared to care as usual by the differences in proportions of self-reported care at six months following corrections release.
3. To assess the acceptability of TCACs to ex-inmate participants and to implementing staff

The secondary objectives of this study are:

1. To assess the effectiveness of TCACs compared to care as usual with regards to:
  - Verified in care at six months
  - Time to linkage to care
  - Linkage to care within 90 days of corrections release
  - HIV RNA <400 c/mL at six months
  - Social capital score change
  - Stigma index score change
  - Employment or self-employment

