### 2.8.4 TCAC eligibility

All study participants assigned to the TCAC arm will be eligible for the TCAC. This includes individuals who may not meet community adherence club eligibility criteria. The reason for this approach is that, at present, there is low linkage to care from corrections. Furthermore, those individuals with the greatest adherence and clinic attendance challenges are hypothesized to benefit the most from the TCAC interventions. Thus all released inmates who meet the enrollment criteria will be eligible for TCACs – this is a critical component of the study.

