**Table 4 : Sample size for TCAC evaluation**

Arm	Sample size
Care as usual	60
TCAC	120

Recruiting 120 in the TCAC arm will provide four TCACs with 12-20 participants each (assuming 40 to 66% successful transition in care to TCACs among participants in that arm). The 1:2 enrollment provides a greater population in the TCAC arm for assessing acceptability. This sample size has an 80% power with an alpha of 0.05 to identify an approximate difference in proportion meeting the primary outcome (in care with an undetectable viral load at 6 months) of 0.24 (e.g. 0.25 versus 0.49 meeting the primary outcome) assuming successful outcome ascertainment for 78% of participants (our success in a prior study) (Figure 2). We note that this is not an effectiveness study and we present these calculations purely to illustrate the power.

[figure not shown]

Figure 2: Proportions in care in CAU and TCAC that study is powered to detect with alpha of 0.05

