### 4.2.2 Effectiveness

Effectiveness will be based on intention to treat comparing CAU and intervention group outcomes using assessed using mixed effects logistic regression with correctional facility included as a mixed effect.

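### Table 3 compares viral suppression between arms only among those in care, a group formed after randomisation, although the objective and outcome list set no such restriction

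*Combined protocol and SAP*

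**What the plan says.** - **Table 3** (section 2.9.2) lists "HIV RNA <400c/mL for those in care by arm" as a secondary effectiveness outcome, tested by chi-square. The table has separate rows for self-reported and record-verified care at six months, and the viral-load row does not say which of the two it means.
- **Section 1.2** gives the matching secondary objective as "HIV RNA <400 c/mL at six months". Secondary outcome 4 in section 2.9.2 is worded in the same way and says routine results will be "augmented by viral loads obtained by the study when 6 month viral load data are not available". Neither limits the outcome to people in care, and neither names a denominator.
- **Section 4.2.2**: "Effectiveness will be based on intention to treat comparing CAU and intervention group outcomes".
- **Sections 2.4.1 and 2.7.2** include a six-month viral-load draw in the consent discussion and plan a study sample at Day 182 when no suitable clinic result exists. Neither makes the draw depend on care status.
- **Section 2.9.2** makes self-reported care at six months the primary outcome, analysed in all randomised participants. It then adds: "We will also perform an eligible for 6 month follow-up analysis".
- **Sections 2.9.1 and 4.2.1** set a target of at least 95% viral-load ascertainment among participants in care, and Table 2 has an indicator worded in the same way.
- **Section 1.2** gives the future full trial a "primary outcome of being in care with an undetectable viral load six months after release", and the power statement in section 4.1 uses the same composite ("in care with an undetectable viral load at 6 months"). It is not among the pilot's own objectives or outcomes.

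**The concern.** Randomisation makes the two arms comparable as a whole. It does not make those still in care at six months comparable, because staying in care is what TCAC is meant to change. The plan gives its own reason to expect different mixes of people: "those individuals with the greatest adherence and clinic attendance challenges are hypothesized to benefit the most from the TCAC interventions". If that is right, the TCAC in-care group will include people who would have been out of care under care as usual.

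The row also removes the route by which TCAC is most likely to act. If TCAC suppresses more people by keeping more of them in care, a comparison restricted to those in care does not count that gain. The pilot's viral-load result could then mislead the design of the full trial, whose planned outcome combines care and suppression.

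**Working it through.** **1. The plan's own figure.** Section 4.1 gives 80% power for 0.25 versus 0.49 on the composite, with 60 and 120 participants and 78% ascertainment. That leaves 60 × 0.78 = 46.8 and 120 × 0.78 = 93.6. The check uses a two-sided test at 0.05 (sidedness is not stated), pooled variance and no continuity correction:
- pooled proportion = (46.8 × 0.25 + 93.6 × 0.49)/140.4 = 0.41
- SE under the null = √[0.41 × 0.59 × (1/46.8 + 1/93.6)] = 0.0881
- SE under the alternative = √[0.25 × 0.75/46.8 + 0.49 × 0.51/93.6] = 0.0817
- z = (0.24 − 1.96 × 0.0881)/0.0817 = 0.825, so power is 79.5%.

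The stated 80% reproduces, for an outcome that has no row in Table 3.

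**2. Inputs for the illustration.** The documents give no suppression rates, so all of those are assumed. For the share in care, the nearest figures are 44% ART continuity at six months in earlier work (section 1.1) and 66%, the upper end of the assumed range for transition to TCAC (section 4.1). Neither is the pilot's definition of in care.

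**3. Equal suppression of 80% among those in care.**
- Table 3 row: 0.80 − 0.80 = 0 points. A test of a true zero is significant about 5% of the time.
- Composite: 0.44 × 0.80 = 0.352 versus 0.66 × 0.80 = 0.528, a difference of 17.6 points. Power at 47 and 94 ascertained is about 51%.
- Suppression among everyone, if a share u of those out of care is suppressed: 0.176 − u × (0.66 − 0.44), which is 17.6, 13.2 or 8.8 points at u = 0, 0.2 or 0.4.

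**4. Extra people retained by TCAC suppressed at rate x, the others at 80%.** Suppression among those in care under TCAC is (0.44 × 0.80 + 0.22x)/0.66, and the composite difference is 0.22x.

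| x | TCAC in-care suppression | Table 3 difference | Composite difference |
|---|---|---|---|
| 0.90 | 0.833 | +3.3 points | 19.8 points |
| 0.80 | 0.800 | 0 | 17.6 |
| 0.70 | 0.767 | −3.3 | 15.4 |
| 0.60 | 0.733 | −6.7 | 13.2 |

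**5. The same check on the 0.25 versus 0.49 example.** At 80% suppression, the care-as-usual share in care is 0.25/0.80 = 0.3125. The extra share retained is 0.24/x, so TCAC in-care suppression is 0.49/(0.3125 + 0.24/x) = 0.846, 0.800, 0.748 or 0.688 for x = 0.90, 0.80, 0.70 or 0.60. Table 3 shows +4.6, 0, −5.2 or −11.2 points, while the composite stays at 24 points (80% power).

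**6. Numbers left in the row.** With 44% and 66% in care, the row holds 60 × 0.44 = 26.4 and 120 × 0.66 = 79.2 people, or 20.6 and 61.8 at 78% ascertainment. At 80% suppression the 95% half-width is 1.96 × √(0.16/26.4 + 0.16/79.2) = 0.176, or 0.199 at the smaller numbers.

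**The case against.** The in-care focus may be deliberate. The feasibility target and a Table 2 indicator also tie viral load to being in care. That stands as an explanation, but those places concern how often a viral load is obtained, not a between-arm effect.

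Sections 2.9.2 and 4.2.2 can together be read as already planning an intention-to-treat viral-load analysis. That also stands: a reader might infer that the plan has no such analysis, and the documents do not go so far. Table 3 conflicts with that reading and leaves open which analysis governs.

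A reader might infer that the row is biased against TCAC. The documents do not show this. Section 2.8.4 says who may benefit most, not that those people will be less suppressed once retained, and at 90% suppression among them the difference favours TCAC.

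A reader might also count the missing composite row as an error. Section 1.2 assigns the composite to the future trial, and section 2.9.2 does not list it, so its absence from Table 3 is consistent with the outcome list.

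Finally, this is a secondary row in a pilot, and section 4.1 says the power figures are only illustrative. Suppression among those retained is also a fair planning question. Both points limit the consequence; neither makes the in-care test a randomised comparison.

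**Conclusion.** The point holds as an unreconciled denominator with a real consequence. As written, Table 3 tests suppression in a group defined by the pilot's primary outcome, against the wording of sections 1.2, 2.9.2 and 4.2.2. With the stand-in shares, the row ranges from about −7 to +3 points while the composite favours TCAC by about 13 to 20. With the section 4.1 example it ranges from about −11 to +5 points against 24. These sizes rest on assumed suppression rates of 60 to 90% and on imperfect figures for being in care. They show what the row can miss, not what it will show. A reversal is possible but not established. The change should be made before analysis, but it does not threaten the pilot's feasibility aims.

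**What to change.** 1. Replace the Table 3 row with HIV RNA below 400 c/mL at six months by arm, among all randomised, to agree with sections 1.2, 2.9.2 and 4.2.2.
2. State one main rule for missing viral loads (for example, not ascertained counts as not achieved), with an ascertained-only sensitivity analysis. Report ascertainment by arm.
3. Keep suppression among those in care as a descriptive figure, without a between-arm test, and say whether in care is self-reported or record-verified.
4. As a low-cost addition rather than a correction, report by arm the composite of being in care with HIV RNA below 400 c/mL.

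**Cost.** The edits are one reworded row, one added row and a short rule; the draw is already planned. The real cost is missing data. Under section 2.7.4, TCAC-arm samples are taken at the TCAC, so people out of care depend on the in-person Day 182 contact in section 2.7.2, and more of their results will be missing. The rule can itself move the estimate. Counting not ascertained as not achieved, at 78% ascertainment in both arms, shrinks 24 points to 0.78 × 24 = 18.7 (power about 74%). With an assumed 70% versus 82% ascertained and 40% suppressed in both arms, the rule alone creates 0.40 × 12 = 4.8 points. That is why both analyses and ascertainment by arm are needed.

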### 2.5 Pre-release study procedures

All participants will have a baseline demographic, health, and incarceration history questionnaire. In addition the ASSIST substance use tool, social capital questionnaire, and stigma index will be used with all participants. Participants will have a second pre-release contact with study staff if release is more than one week from enrollment. The purpose of this visit will be to review the study, the allocation arm, and to encourage linking to care following release.

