## 2.7.2 Ascertainment of linkage to care

Study staff will contact participants to ascertain care status and update contact information at 30, 90 and 182 days from release. Follow up will primarily be telephonic and will rely on participant self-report. The scheduled visit windows are: Day 30 (from 20-70 days), Day 90 (from 71-150 days), and Day 182 (from 151 – 245). The last contact attempt will be made on Day 246. At the Day 182 visit, participants will be asked for in-person contact that will occur either at research offices or at a site convenient to the participant. This study visit will be used to ascertain visit status, socio-demographic data, and to complete surveys on stigma, social capital, and care satisfaction. In addition, a whole blood sample (8mL) will be obtained for HIV RNA quantification (viral load) if there are no clinic obtained HIV RNA results from within 60 days or 182 days post-release. Refer to schedule of CRFs for data collection tools used at each study visit.

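### Social capital and stigma are defined as score change, but Table 3 tests an unadjusted score by arm with no baseline or time point

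*Combined protocol and SAP*

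**What the plan says.** The secondary objectives in section 1.2 include "Social capital score change" and the same for stigma. Section 2.9.2 repeats both as items 5 and 6 of its list, the second as "Stigma index score change".

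Table 3, at the end of section 2.9.2, assigns a test to each outcome. Its rows for these two read "Social capital score by arm" and "Stigma index score by arm", each with a Wilcoxon rank sum test. Neither row mentions change, a baseline value or a time point.

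Both instruments are given before release to both arms. Section 2.5 says that the "social capital questionnaire, and stigma index will be used with all participants", and Table 6 makes the pre-release assessment form (RK001) mandatory at enrolment. Section 2.7.2 uses the Day 182 in-person visit "to complete surveys on stigma, social capital, and care satisfaction".

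The rest of the plan supplies no analysis that uses the pre-release scores. Section 4.2.2 describes only a logistic model with a facility effect. Section 5.3.5 mentions covariates only for logistic regression and does not name these scores.

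**The concern.** The stated outcome and the tabled variable differ for both scores. Two analysts working from this plan could test different quantities and report each under the same outcome name. If Table 3 is followed to the letter, a comparison of follow-up scores would be reported as a comparison of change, and a baseline measurement taken from every participant would not be used.

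This matters because the two scores are the plan's measures of part of its proposed mechanism. Section 6.2 lists an increase in social capital among the effects under study. The pilot is also meant to produce a protocol ready for a full trial, so an unsettled score analysis could pass into that trial.

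**Working it through.** **Inputs.** Arms of 60 CAU and 120 TCAC (section 4.1, Table 4); 78% outcome ascertainment (section 4.1). The documents give no SD for either score and no correlation *r* between the pre-release and six-month values. Results are therefore in SD units, and *r* is an assumption shown at 0.3, 0.5 and 0.7. Equal SDs at the two times are also assumed.

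**The plan's own figure.** The plan gives no precision or power for the scores. Its one power statement (80% for 0.25 versus 0.49, section 4.1) concerns a binary outcome. It reproduces with 0.78 × 60 = 46.8 and 0.78 × 120 = 93.6:
- pooled proportion = (0.25 × 46.8 + 0.49 × 93.6)/140.4 = 0.41
- SE under no difference = √[0.41 × 0.59 × (1/46.8 + 1/93.6)] = 0.0881
- SE under the alternative = √(0.25 × 0.75/46.8 + 0.49 × 0.51/93.6) = 0.0817
- power = Φ[(0.24 − 1.96 × 0.0881)/0.0817] = 79.5%

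This supports using the 78% figure but says nothing about the scores.

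**Standard error of the arm difference, in SD units.** With the counts rounded to 47 and 94:
- follow-up score: √(1/47 + 1/94) = 0.179
- change score: 0.179 × √[2(1 − r)]
- follow-up score adjusted for baseline: 0.179 × √(1 − r²)

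| Assumed r | Follow-up score | Change | Baseline-adjusted |
|---|---|---|---|
| 0.3 | 0.179 | 0.211 | 0.170 |
| 0.5 | 0.179 | 0.179 | 0.155 |
| 0.7 | 0.179 | 0.138 | 0.128 |

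Change beats the follow-up score only when 2(1 − r) < 1, that is, when r > 0.5. For any r between 0 and 1, the adjusted analysis has smaller variance than both: the ratio is 1 − r² against the follow-up score and (1 + r)/2 against change.

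**With the test that Table 3 names.** Assuming normal scores, the rank sum test has relative efficiency 3/π. The detectable difference at 80% power and two-sided 0.05 is (1.960 + 0.842) × √(1/46.8 + 1/93.6) = 0.502 SD for a mean comparison. Dividing by √(3/π) gives 0.51 SD for the Wilcoxon test on the follow-up score. At r = 0.3, 0.5 and 0.7, the Wilcoxon test on change detects 0.61, 0.51 and 0.40 SD, and the adjusted linear model 0.48, 0.43 and 0.36 SD.

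**The adjusted difference is also a difference in change.** If six-month score = a + b·arm + c·baseline, then subtracting baseline from both sides gives change = a + b·arm + (c − 1)·baseline. The arm coefficient b is the same, so the adjusted model serves the outcome as sections 1.2 and 2.9.2 name it.

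**The case against.** The strongest reply is that the rows are shorthand. Table 3 follows directly on the list that defines these outcomes as change, and it is abbreviated elsewhere: the employment row has no time point, and time to linkage is missing. A rank sum test of each participant's change, by arm, would be valid and would use the baseline. This stands as far as it goes. A reader might infer that the plan definitely tests the raw follow-up score and discards the baseline, but the documents do not settle that. What they show is that the row does not say which variable is tested, and that neither reading adjusts for baseline.

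Second, randomization makes the expected pre-release difference zero, so the follow-up comparison and the change comparison are both unbiased, and their mean differences agree in expectation. This stands in full. A reader might infer that a chance imbalance at release biases the result or passes whole into it. It does not: it is random error that the test already allows for, and with equal SDs only a fraction r of it carries into the follow-up score on average.

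Third, the correlation may be low. Enrolment is 1 week to 3 months before release and the last visit window opens at day 151. The two measurements are thus at least 7 + 151 = 158 days apart and straddle the release itself. At r = 0.3 adjustment only moves the standard error from 0.179 to 0.170 SD. This also stands, and it rules out quoting the gain at r = 0.7 as the expected benefit. It equally counts against simply inserting the word change in Table 3, which at r = 0.3 would raise the standard error to 0.211 SD.

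Fourth, the remedy makes a linear model the main analysis in place of a rank test. That is a real trade, and a prespecified rank-based sensitivity analysis answers it.

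**Conclusion.** The mismatch between the defined outcome and the tabled variable is real and applies to both scores, and nothing elsewhere in the plan resolves it. Its consequences are a possible mislabelled result and avoidable imprecision, not bias. Relative to the follow-up score, baseline adjustment lowers the standard error by about 5%, 13% or 29% at r = 0.3, 0.5 or 0.7 (1 − √(1 − r²)). Relative to change, it lowers it by about 19%, 13% or 8% (1 − √[(1 + r)/2]). These figures rest on 78% ascertainment, equal SDs and a correlation that the documents do not give.

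Severity is modest. These are two of seven secondary outcomes in a pilot that disclaims being an effectiveness study, and the feasibility indicator on completing the six-month questionnaires is unaffected. The change is still worth making because the baseline scores are already collected and it can be settled before outcome data are seen.

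**What to change.** In Table 3, replace both rows with: six-month (Day 182) score adjusted for pre-release score and correctional facility, by arm. Use one prespecified linear model for each score and report the adjusted difference with its 95% CI. The outcome names in sections 1.2 and 2.9.2 can stay if a note says that this is also the adjusted difference in change.

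Add the model to section 4.2.2, which now covers only binary outcomes. Facility belongs in it because randomization is blocked by facility and the existing logistic model already includes it.

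Name Day 182 explicitly. Table 5 also schedules these instruments on the post-release assessment form (RK002), at Day 30 in CAU and at the first session in TCAC, so a score by arm without a time point is open to more than one reading.

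Prespecify either a rank-based ANCOVA or the Wilcoxon test as a sensitivity analysis. Do not make it a switch triggered by observed skewness: that would let the data choose the main analysis, and rank ANCOVA does not give a difference in score units.

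The cost is two table rows, one sentence in section 4.2.2, and reliance on a linear model for the main result. No new data are needed and there is no added burden on participants or sites.
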